Power analysis: Power calculations for Aim 1, hypothesis 1 of this study were based on a repeated measures design (2 sided $\alpha = .05$) with 2 treatment groups (DSME+ Mind-STRIDE; DSME-Alone) and 3 time points (baseline, 12 weeks post intervention, 24 weeks post-intervention). We computed sample size estimates that were powered to detect an overall treatment group difference in DRD (PAID scale score) as well as a treatment group difference over time (interaction between treatment group and time). Based on our pilot work, a medium effect size ($d = .6$) gives a clinically meaningful change in PAID score. Using a medium ($d = .5$) effect size, and estimates of the correlations between observations on the same subject of $r = .5$, powering at 80% gives a sample size estimate of 86 (~43 per group). To account for possible clustering due to the randomization occurring in groups of $n = 5$ participants, the required total sample size (86) was inflated by a factor of $(1 + (5-1) * p)$, where p is the intra-cluster correlation coefficient.^{78, 79} A conservative estimate of the intra-cluster correlation of $p = 0.05$, gives an increased sample size of 104 (~52 per group). To ensure a sample of 104 at study completion, 126 Veterans will need to be recruited over the 2-year study period. This number of 126 Veterans is approximately 20% of the usual number of Veterans referred for DSME over two years and is within what is considered reasonable to recruit based on our pilot data. Sample size estimates were computed in Stata Statistical Software: Release 12 (College Station, TX: StataCorp LP; 2011).

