[name] PhD, Associate Professor of Biostatistics at the University of Pittsburgh Graduate School of Public Health, will oversee statistical analysis for Aim 1. Analyses for Aim 1 will be performed using Stata statistical software. Diabetes distress (the primary outcome) and secondary outcomes (mindfulness diabetes self-efficacy, diabetes self-management, and HbA1c) will be assessed for normality and appropriate data transformations will be used if necessary. Descriptive statistics will be computed to determine central tendency, data sparseness, and existence of outliers for all other continuous variables. Frequency distributions will be generated for categorical variables to identify data sparseness, and categories with small frequencies will be merged when appropriate. In addition, we will consider categorization of continuous predictors if the distributions are skewed or violate assumptions of linearity. Differences in covariates by treatment group will be tested using chi-square (or Fisher's exact) statistics for categorical variables and t-test (or Mann-Whitney) for continuous variables. Graphical procedures will be used to assess simple change in the outcomes over time. For the main analyses for Aim 1, we will test study hypotheses by using linear mixed models (or non-linear

mixed models where appropriate), which account for repeated measures and assess change over time (baseline, 12 weeks, 24 weeks). The linear mixed model allows for missing data if data are missing at random. Demographic variables with a univariate association with the outcome ($p < 0.10$) or differed by treatment group at baseline ($p < 0.05$) will be considered for inclusion in a multivariate model. Covariates will be retained in the final multivariable models if significant at $p < 0.05$. All tests will be two-sided. All analyses will be conducted as intent-to-treat analyses and include all patients in the groups to which they were randomized, regardless of adherence and/or subsequent withdrawal.

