Missing Data. We will review all assessments for completeness during the session in which it is collected to attempt to minimize missing data for Aim 1. We will attempt to assess the missing data mechanism for missing data due to lost to follow-up or withdrawal. If there are significant differences in baseline variables between those subjects that have complete outcome data and those that do not, we will adjust for those covariates as part of the modeling.⁸⁰ If no systematic differences are found or if the missing data is intermittent, the missingness will be handled as part of the regression modeling. Using linear mixed linear models allows the use of all available data, including data from those who are missing one or more of the assessments. We will also perform completers only analyses and see if these differ compared to the modeling using all of the available data to assess sensitivity to the missingness.

3.7.2 General Analytic Approach for Aim 2

Aim 2: To identify Veteran satisfaction and experiences with DSME +Mind-STRIDE.

We will use Convergent Parallel Design (Figure 5) to develop a more complete understanding of the research questions by obtaining different but complementary quantitative (Aim 1) and qualitative (Aim 2) data.⁸¹ Collecting and analyzing two independent strands of data at the same time in a single phase will enable us to prioritize the methods equally while keeping the data analysis independent. We will then mix the results at the point of interface, looking for convergence, divergence, contradictions or relationships of the two sources of data that will inform the overall interpretation of study results.

[figure not shown]

Figure 5. Convergent Parallel Design

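### The only planned check on missing data does not relax missing at random, so its agreement with the mixed model would say little about outcome-related dropout

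*Combined protocol and SAP*

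**What the plan says.** All statements are in the combined protocol and SAP, section 3.7.1.

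- **Target.** Analyses are intent-to-treat. Everyone counts in the arm to which they were randomised, whether or not they adhere or withdraw.
- **Primary model.** PAID at baseline, week 12 (T2) and week 24 (T3) goes into a linear mixed model with arm, time and their interaction. Its missing-data basis is stated: "The linear mixed model allows for missing data if data are missing at random".
- **Missing Data paragraph.** The team will try to assess the missing-data mechanism. If people with and without complete outcomes differ at baseline, those variables enter the model. Otherwise the missingness is left to the regression model.
- **Sensitivity analysis.** One is named: "We will also perform completers only analyses and see if these differ compared to the modeling using all of the available data". Its stated purpose is to judge sensitivity to the missingness.
- **Expected loss.** The Power analysis paragraph gives no dropout rate, only "To ensure a sample of 104 at study completion, 126 Veterans will need to be recruited over the 2-year study period".

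The text contains no delta-adjusted, tipping-point, reference-based or pattern-mixture analysis.

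**The concern.** A sensitivity analysis is useful when it relaxes the assumption on which the primary analysis depends. This one generally tightens it. The mixed model lets dropout depend on PAID scores already observed. Completers-only needs those who finish to represent their whole arm, given the covariates in the model. Adjusting for baseline variables uses observed data only, so it also stays within missing at random.

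The case left untested is dropout related to the unseen PAID score, for example people in the experimental arm who leave because the programme is not helping. Features of the trial make different dropout in the two arms conceivable. Section 3.6.3 puts the time burden at about 30 hours in the experimental arm and about 5 in usual care. Under section 3.4 the experimental arm receives the tablet after the first session, while controls receive it only after T3. The outcome is self-reported by people who know whether they had the mindfulness training. If such dropout occurs, the estimate can miss the intent-to-treat target, and close agreement between the two planned analyses would give no warning.

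**Working it through.** **Inputs from the Power analysis paragraph.** Two-sided alpha 0.05, power 80%, d = 0.5, within-person correlation r = 0.5, three time points, clusters of 5 with intra-cluster correlation 0.05.

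**1. Reproduce the plan's sample sizes.** For a comparison of the mean of three measures, the variance factor is (1 + 2r)/3 = 0.667. Then n per arm = 2 × (1.960 + 0.842)² × 0.667 / 0.5² = 41.9, so 42 by the normal approximation and 43 with the t distribution. That gives 86 in total, as stated. The design effect is 1 + 4 × 0.05 = 1.2, and 86 × 1.2 = 103.2, or 104 at 52 per arm, as stated.

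**2. Implied dropout.** 1 − 104/126 = 17.5%. This is a back-calculation from the recruitment allowance, and I assume that it applies to the experimental arm.

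**3. Bias when the lost benefit is never observed.** Let m be the share of the experimental arm without a week-24 PAID score, and k the share of the benefit that those people keep. Assume that they are otherwise like completers and that control dropout is unrelated to outcome. The effect in all randomised is 0.50 × [1 − m(1 − k)], while both planned analyses return about 0.50. The overstatement is 1/[1 − m(1 − k)] − 1.

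| m | k | Effect in all randomised | Overstatement |
|---|---|---|---|
| 17.5% | 0 | 0.50 × 104/126 = 0.413 | 21.2% |
| 17.5% | 0.5 | 0.456 | 9.6% |
| 17.5% | 0.75 | 0.478 | 4.6% |
| 10% | 0 | 0.450 | 11.1% |
| 10% | 0.5 | 0.475 | 5.3% |
| 25% | 0 | 0.375 | 33.3% |

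**4. Opposite direction.** If those who leave had one and a half times the benefit (k = 1.5, m = 17.5%), the result is 1/(1 + 0.175 × 0.5) − 1 = −8%, an understatement.

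**5. Simulation.** I used 300,000 participants, SD 1, r = 0.5, an effect of 0.5 at weeks 12 and 24, and k = 0. The mixed model was fitted by maximum likelihood with unstructured covariance, and the contrast was change from baseline to week 24.

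| Dropout, and when the benefit is lost | Mixed model | Completers-only |
|---|---|---|
| 17.5% per arm, all before week 12 | +20.1% | +20.0% |
| 17.5%, half before and half after week 12; lost on leaving | +20.1% | +20.1% |
| 17.5%, all after week 12; lost on leaving | +20.4% | +20.9% |
| 25% experimental, 10% control, all before week 12 | +33.0% | +32.7% |
| 17.5%, half after week 12; loss already seen at week 12 | +18.0% | +22.0% |
| 17.5%, all after week 12; loss already seen at week 12 | +14.7% | +21.7% |

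The one-point gap from the closed form is of the order of simulation noise; with k = 1, where no bias exists, both analyses showed +0.5%.

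**6. Why the last row separates.** With r = 0.5, the regression weight of week 24 on week 12, given baseline, is r/(1 + r) = 1/3. Dropouts seen without benefit at week 12 are 0.5 worse than completers there, so the model predicts an effect of 0.50 − 0.5/3 = 0.333 for them. The estimate is 0.50 − 0.175 × 0.167 = 0.471, which is 14.1% above 0.413. The mixed model recovers only part of the loss.

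**The case against.** The strongest reply is that the comparison does have information. If people leave because they are not benefiting, and this shows at week 12, the mixed model uses those scores and completers-only discards them, so the two differ. That stands. A reader might infer that the two analyses must always give the same biased answer, or that completers-only should be removed. The last two rows of the simulation table support neither. The mixed model is nevertheless still 14–15% too high in the last row, and the comparison does not show by how much.

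Second, stopping home practice is not the same as a missing outcome. Much of the experimental arm's burden is home practice, and someone who gives it up can still be assessed and is analysed as randomised. Only missing PAID scores create this bias. The plan works to limit them, with payments rising to 75 and 100 dollars, monthly postcards (section 3.4) and completeness checks at each session. This stands, and it may keep the loss below 17.5%.

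Third, a reader might take 20% as the expected bias. The documents do not support that. They give no dropout rate, nothing on dropout by arm and nothing on how dropouts fare. The text available of section 1.7.4 describes pilot retention favourably without a rate, and part of that section was not available to check.

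Fourth, a reader might infer that the plan treats agreement as proof of robustness. It states no such rule; it says only that the analyses will be compared. The criticism is that no interpretation is given and that agreement could bear little weight.

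**Conclusion.** The point holds as a gap in the sensitivity analysis. It is not an error in the primary model. Every missing-data step in section 3.7.1 either assumes missing at random or assumes more, so the plan cannot show how far the T3 result depends on that assumption.

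The size is conditional. With an assumed 17.5% of the experimental arm missing and d = 0.50 in completers, the overstatement runs from about 5% (three quarters of the benefit kept) to 21% (none kept). It reaches 33% with 25% missing and none kept. These figures also assume that the lost benefit is not seen before dropout and that control dropout is unrelated to outcome. The sign reverses if improvers leave. This is a worthwhile, inexpensive improvement.

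**What to change.** Keep the mixed model as primary, and keep completers-only as a descriptive comparison. Add to the Missing Data paragraph:

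- Multiple imputation of missing T2 and T3 PAID from arm, baseline PAID, any observed T2 PAID and the model covariates.
- A shift (delta), in PAID points, added to the imputed values. Vary it separately in each arm and in both directions, over a range fixed in advance.
- A report of the shift, or pair of shifts, at which the T3 conclusion changes, beside the number and timing of missing scores by arm.

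For shifts applied to the week-24 values, the contrast moves by m_E × δ_E − m_C × δ_C, where m is the share missing in each arm. In the k = 0 case above, a shift of 0.5 SD in the experimental arm moves it by 0.175 × 0.5 = 0.087, from 0.50 to 0.413. Control-based imputation may be added as an optional scenario, with its own assumption stated: that experimental dropouts behave like controls.

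Settle this before anyone sees outcomes by arm. It needs no extra participants, visits or measures. The costs are SAP wording, modest programming, and a sensitivity result that may be less favourable than the primary one.

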3.8 Timeline

[name], the Principal Investigator (PI), will be oversee the details of the study including hiring and training staff, testing the data entry system, creating study manuals, and recruiting and consenting subjects. She will lead weekly meetings with the Research Team and bi-monthly meetings with Co-Investigators so that issues can be addressed in a timely manner. The Mentoring team is highly experienced in conducting clinical trials, and will guide the investigator in reaching charted milestones on the timeline. See Gantt chart (Table 6).

Table 6. Study Timeline

Study Activity	Year 1				Year 2				Year 3			
	Q1	Q2	Q3	Q4	Q1	Q2	Q3	Q4	Q1	Q2	Q3	Q4
Conduct monthly team meetings	X	X	X	X	X	X	X	X	X	X	X	X
Hire staff	X	X										
Create procedure manual	X	X										
Create data entry system	X	X										
Recruit participants		X	X	X	X	X	X	X	X			
Deliver intervention		X	X	X	X	X	X	X	X	X		
Collect data			X	X	X	X	X	X	X	X	X	
Analyze data			X	X	X	X	X	X	X	X	X	
Prepare and submit publications a presentations									X	X	X	X

3.9 Study Design Considerations

Several aspects of the study design warrant consideration. First, the 3-year duration of the study prevents extended follow-up of more than 6 months. However, based on previous research of DSME and mindfulness interventions, we expect to be able to detect changes in the outcomes specified, and the 6-month time period is consistent with typical clinical follow-up periods. Second, there is potential for adjustment of diabetes medications during the study by care providers. To account for this, medication will be tracked and verified in CPRS, and controlled for in the analysis. Finally, generalizability is limited due to the relatively small sample size and single VAMC site. However, our site is a large academic medical center serving a range of diabetes severity in a Veteran population drawn from urban, suburban, and rural areas in the region. Additionally, the proposed study includes a qualitative component, for which the purpose is not generalizability, but rather gaining an understanding of a phenomenon of interest in a specific group of participants.⁸⁷

Particular advantages of our study design and approach include the fact that the intervention has been pilot-tested at VAPHS and fit into the already existing DSME format and therefore can realistically be implemented without delay. Additionally, to the extent possible, one trained diabetes educator will deliver the DSME component and one trained mindfulness instructor will deliver the Mind-STRIDE intervention to all groups in order to decrease instructor bias. In order to sustain engagement in the study, all participants will receive monthly postcards from the research study. Control group participants will receive postcards with healthy tips for living with diabetes, and experimental group participants' postcards will include these tips plus mindfulness tips and quotations. And finally, our mixed-methods methodology will provide a more comprehensive evaluation of the program and inform potential implementation at other VAMCs in the future.

To assure that the mindfulness training is delivered in a standardized way, a course manual will be developed and instructor guidelines will be followed. Pursuant to IRB approved authorization, all Mind-STRIDE sessions will be audiotaped using a VA-approved encrypted audio-recorder. [name], our mindfulness expert, will develop a fidelity-rating guide for the intervention. [name] will train the Study Coordinator to use this guide to assess the fidelity of each audio-recorded session, so that the interventionist can be made aware of any discrepancies from the course manual, and they can be corrected in a timely fashion.

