3.4.1 Randomization Procedure

After screening and written informed consent procedures have been completed, all eligible research participants entering the study will complete baseline procedures. After baseline assessments are completed, participants will be randomized into one of two groups: 1) DSME + Mind-STRIDE (the experimental group), or 2) DSME-Alone (usual care). The study statistician will perform the randomization process using statistical software with a random-number generator to create a list of group assignments before study recruitment begins. Randomization will occur in blocks of 4 or 6, and the group assignments will be created based on the specific number of expected eligible participants.

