3.5 Description of Usual Care and Experimental Conditions

Participants in both conditions will continue their usual diabetes care as per their diabetes care providers. They will self-monitor their blood glucose according to instructions provided by their diabetes care providers, and will transmit data from their home blood glucose meters using standard VA issued Home Tele-Health equipment that is available and offered to all patients.

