3.7 Data Analysis

3.7.1 General Analytic Approach for Aim 1:

Aim 1: To compare the effects of the intervention (DSME+ Mind-STRIDE) with those of usual care (DSME-alone) on diabetes distress, diabetes self-efficacy, and DSM in military Veterans over time.

Hypotheses. From baseline to 24-week post-intervention, DSME+ Mind-STRIDE compared to DSME-Alone will:

1. Significantly reduce DRD (primary outcome)
2. Significantly increase mindfulness, diabetes self-efficacy and diabetes self-management (secondary behavioral outcomes)
3. Significantly decrease HbA1c (distal metabolic outcome)

Independent variable: The Mind-STRIDE intervention, which includes mindfulness stress reduction, mindfulness meditation training and home practice.

Dependent variables: The primary outcome on which the analysis is powered is DRD measured by the PAID scale. Secondary outcomes include diabetes self-efficacy, diabetes self-management, mindfulness, and glycemic control, measured by HbA1c.

Analysis: To assess whether there are group differences over time, we will use separate linear (or non-linear depending on outcome) mixed models for each outcome (diabetes distress, primary), diabetes self-efficacy, diabetes self-management, mindfulness and glycemic control (secondary) for 3 time points (baseline, 12 weeks post-intervention, and 24 weeks post-intervention). The base model will include fixed effects for treatment group DSME+ Mind-STRIDE, DSME-Alone group, time, and the interaction between treatment group and time. To the extent possible, post-hoc analyses to explore the possible relationships between mindfulness and diabetes-related distress (as well as the interaction between them) on the distal secondary outcome, glycemic control will be performed.

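### Section 3.9 commits to adjusting for diabetes medication changes made after randomisation. If the arms differ in those changes, an HbA1c model adjusted for them no longer estimates the total effect of assignment.

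*Combined protocol and SAP*

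**What the plan says.** Section 3.9 notes that "there is potential for adjustment of diabetes medications during the study by care providers", and responds that "medication will be tracked and verified in CPRS, and controlled for in the analysis". It names the data source but no outcome, model term or coding, and does not say whether this is a main or a sensitivity analysis.

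The other relevant places are these:

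- **Section 3.4.1:** "After baseline assessments are completed, participants will be randomized into one of two groups". Changes made during the study therefore come after assignment.
- **Section 3.5:** "Participants in both conditions will continue their usual diabetes care as per their diabetes care providers".
- **Section 3.7.1, hypotheses:** the third predicts lower HbA1c in the experimental arm. HbA1c is a secondary outcome.
- **Section 3.7.1, model for every outcome:** "The base model will include fixed effects for treatment group DSME+ Mind-STRIDE, DSME-Alone group, time, and the interaction between treatment group and time". It has no medication term.
- **Section 3.7.1, covariate screen:** this begins with "Demographic variables with a univariate association with the outcome". Section 3.6.1 lists medication on the demographic questionnaire, but Table 5 schedules that questionnaire at T1 only.
- **Section 3.7.1, missing data:** the adjustment described there uses baseline variables.
- **Section 3.7.1, analysis set:** "All analyses will be conducted as intent-to-treat analyses and include all patients in the groups to which they were randomized".

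**The concern.** Adjusting for a baseline covariate leaves the treatment effect's meaning intact in a linear model. Adjusting for something that happens after randomisation may not. Providers in both arms remain free to change medication. If the intervention lowers HbA1c, they may have less reason to intensify treatment in the experimental arm. Medication change would then be partly a consequence of assignment, and holding it fixed removes part of what assignment did.

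The adjusted figure answers a different question: what would the effect be without medication changes? That is a fair question, but a regression term answers it only if the causes of medication change that also affect HbA1c are in the model. No other section confines the Section 3.9 commitment to baseline medication or makes it a sensitivity analysis. Followed as written, it can put the adjusted effect in the place of the main HbA1c result.

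**Working it through.** **The plan's own figures.** None is attached to the medication adjustment. The sample size in Section 3.7.1 is set on PAID: 86, times 1 + (5 - 1) x 0.05 = 1.2, gives 103.2, stated as 104. The point does not alter this; 104 and 1.2 are used below only to scale the result.

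**Inputs.** From the plan: three visits, the group-by-time mixed model, 104 completers, clustering factor 1.2, and within-patient correlation 0.5 (the plan's value for PAID, borrowed here for HbA1c). Assumed, because the documents give no value:

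- HbA1c SD 1.3
- a direct intervention effect of -0.50 points
- medication changed between weeks 12 and 24, likelier at high week-12 HbA1c (log-odds slope 1 per SD)
- 37% changed in control
- a medication effect on week-24 HbA1c of -0.7 or -1.0 points

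**Formula.** With direct effect D, medication effect m, and shares changed pC (control) and pT (experimental):

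total effect = D + m x (pT - pC)

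The model without a medication term estimates this total. A model with a visit-varying medication term estimates D, provided medication change and HbA1c share no unmeasured cause.

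**Medication change driven by HbA1c alone.** The assumed slope and direct effect give about 30% changed in the experimental arm.

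| m | Unadjusted | Adjusted | Difference |
|---|---|---|---|
| -0.7 | -0.50 + 0.7 x 0.07 = -0.45 | -0.50 | 0.05 |
| -1.0 | -0.50 + 1.0 x 0.07 = -0.43 | -0.50 | 0.07 |

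Simulating the planned three-visit model agrees with these figures to about 0.01. With equal rates (37% and 37%) both models give -0.50.

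**Scale.** The standard error of the week-24 group-by-time effect is 1.3 x sqrt(2 x (1 - 0.5)) x sqrt(4/104) = 0.255, or 0.255 x sqrt(1.2) = 0.279 with clustering. Then 0.05/0.279 = 0.18 and 0.07/0.255 = 0.27, so the difference is about 0.2 to 0.3 standard errors.

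**If the arm also affects prescribing directly** (a further assumption):

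- Log-odds -0.8 gives 37% against 18%. With m = -1.0 the estimates are -0.31 and -0.50, a difference of 0.19.
- Log-odds +0.8 with no direct HbA1c effect gives 37% against 53%. With m = -0.7 the estimates are -0.11 and 0.00. With m = -1.0 they are -0.16 and 0.00.

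**If an unmeasured factor drives both medication change and HbA1c,** adjustment no longer recovers D. In the 37% against 18% case, with an assumed driver (log-odds 1.0 per SD, +0.3 on week-24 HbA1c), the estimates are -0.32 and -0.46. The medication coefficient is -0.77 against a true -1.00.

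**Coding.** A changed/unchanged flag held constant per patient and entered as a main effect gives no shift with complete data, because the group-by-time contrast is then a within-patient one. A visit-varying term gives the differences above. Section 3.9 fits either coding.

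**The case against.** The strongest reply is that controlling for medication suits an efficacy trial. The conceptual model in Section 1.5 has HbA1c improving through self-management and stress physiology, and Section 1.4 cites an earlier result found to be independent of medication changes. Removing a rival explanation is legitimate, and declaring the adjusted model as the main one, with its coding, would also end the ambiguity. That stands as a reason to keep the adjusted analysis. It does not make that analysis an estimate of the total effect of assignment, and it still relies on capturing the drivers of prescribing.

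It is also fair that Table 5's lack of a medication row at T2 and T3 proves little, since Section 3.9 names CPRS as the source.

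Some stronger readings are tempting but not supported:

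- **A large distortion.** A reader might infer that the choice commonly moves HbA1c by about 0.2 points. The 0.19 figure needs a direct arm effect on prescribing that nothing in the documents indicates. Medication change driven by HbA1c alone gives 0.05 to 0.07.
- **Free choice of model.** A reader might infer that the sponsor may report whichever model it prefers. Section 3.9 is a flat commitment to adjust, and Section 3.7.1 builds multivariable mixed models on the base model. What is open is which outcomes carry the term, how it is coded, and which model is the main result.
- **A breach of intent-to-treat.** The plan's wording governs who is analysed and in which arm. Adjustment does not violate that; it changes the effect being estimated.

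**Conclusion.** The point holds and should be addressed. Section 3.9 plans to condition on a post-randomisation variable that the intervention may affect, and no other section limits or labels that adjustment. It mainly concerns HbA1c. PAID is affected only if the term enters its model, which the text leaves open.

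Under the stated assumptions the likely size is modest: 0.05 to 0.07 HbA1c points, about 0.2 to 0.3 standard errors. Differences of 0.11 to 0.19 require the extra assumption that the arm itself influences prescribing. If the arms do not differ in medication change, the difference is zero. Apart from the correlation and sample size, these inputs are assumptions, so the figures are illustrations and not predictions for this trial.

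**What to change.** Replace the Section 3.9 sentence with:

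> Medication changes after randomisation will be tracked in CPRS and reported by arm. The main HbA1c model (and the PAID model) will not adjust for on-study medication change and will use all outcome data regardless of it; baseline regimen may be included. A model adjusted for on-study medication change, with its coding fixed before analysis, will be reported as a labelled sensitivity analysis.

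The baseline regimen is already collected on the T1 questionnaire. The change is confined to medication: it leaves the other potential covariates in Section 3.6.1 as they are, and does not touch clinical care or the sample size.

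The cost is a wording change, a coding rule and one descriptive table, all from data the plan already tracks. The downside is that the main HbA1c result will include the effect of any medication changes. The table by arm and the sensitivity analysis let readers judge how much that matters.
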